17. STATISTICAL METHODS AND DETERMINATION OF SAMPLE SIZE

A prospective, randomized (1:1:1), double-blind, multi-center, placebo-controlled clinical study.

Statistical Hypothesis

The hypothesis of this study is that treating with CimetrA and CimetrA2 will be more effective, while maintaining a favorable safety profile. This will be demonstrated by a significant difference between the two active and the control groups.

	MGC Pharma Clinical Study Protocol	Protocol No.: MGC-009
		Version 02, 05 Sep 2021
		Page 60 of 76
A Phase IIb, double blind, placebo-controlled clinical study designed to evaluate the effect of Cimetra in patients diagnosed with COVID-19		CONFIDENTIAL

In this study, we will test the following hypothesis:

- H0: $\Delta_1 = \Delta_2 = \Delta_3$
- H1: at least one is different.

Where Delta is the difference between baseline and end of study in WHO Ordinal Scale for clinical trial.

If the null hypothesis is rejected in favor of the alternative hypothesis the study will be deemed successful.

Safety will be assessed by adverse events, blood and urine laboratory assessments and vital signs.

Planned Sample Size

For this phase IIb, 3-armed clinical trial, we use the ANOVA test to estimate the expected improvement in the primary outcome; the WHO ordinal scale for clinical improvement.

We expect medium effect ($f=0.20$) for the differences in Delta between the 3 groups, and standard deviation of 1.5, based on the ordinal scale (0-8). This power analysis is for a one-way fixed effects analysis of variance with 3 levels. The study will include 80 patients per group for a total of 240 patients.

The criterion for significance (α) has been set at 0.05 with Power of at least 80%.

The analysis of variance is two-tailed Main effects.

For immunogenicity assessment, larger sample size will reduce mean variability in the observed outcomes and will increase the opportunity to detect real changes.

For 80 participants per group we ensure the desired precision for phase 3 trial to assess safety and effectiveness. Total sample 240 patients.

Computer Software

	MGC Pharma Clinical Study Protocol	Protocol No.: MGC-009
		Version 02, 05 Sep 2021
		Page 61 of 76
A Phase IIb, double blind, placebo-controlled clinical study designed to evaluate the effect of CimetrA in patients diagnosed with COVID-19		CONFIDENTIAL

Sample size and Power were calculated with the Power and Precision statistic program ver 4.1 and all statistical analyses and data presentations, including tabulations and listings, will be performed using the SPSS statistic program version 27.0 (or higher) software.

Randomization

Randomization tend to produce study groups comparable with respect to known and unknown risk factors, removed investigator bias in the allocation of participants and guarantees that statistical tests will have valid false positive error rates.

After a participant will meet the eligibility criteria, he/she will be randomly allocated (with a 1:1:1 ratio) to one of the following treatment groups based on a randomization scheme stratified by center.

The randomization scheme will be prepared by an independent statistician using statistic program for random number generator. The block size is set in ahead and study personnel will be blinded to the randomization block size.

Blinding

This is a double-blind study: neither the participants nor the investigators will be aware of arm allocation of each study participant.

Blindness is important to avoid bias. Monitoring and reporting of the success of blindness are important for the reader's confidence of the trial results. Groups should be marked by capital letter and blindness should maintain throughout the study.

Missing Data

Safety data should be collected from non-adherent/withdrawal participants to avoid possible bias.

	MGC Pharma Clinical Study Protocol	Protocol No.: MGC-009
		Version 02, 05 Sep 2021
		Page 62 of 76
A Phase IIb, double blind, placebo-controlled clinical study designed to evaluate the effect of Cimetra in patients diagnosed with COVID-19		CONFIDENTIAL

Prior to analyzing the data, extreme laboratory values should be checked. Missing values will be treated as ITT.

Multiple imputation for binary data will be used as the primary imputation method in the case of missing data for the primary efficacy endpoint.

Dropout/AE Imputation: A participant with no post baseline measurement or a participant withdrawn due to an adverse event or treatment intolerability will use last observation carried forward imputation methods.

Baseline Data

Baseline participant characteristics will be collected at screening. The specific baseline (“start of treatment”) endpoints and other symptoms will be collected prior to each treatment.

Significance Levels and Handling of Type I Error

The overall significance level for this study is 5% using two-tailed tests, except for treatment by center/region interaction that will be tested at a significance level of 10%.

When multiple comparisons between the groups are made, the chance of finding a significant difference in one of the comparisons is greater than the stated significance level, therefore we will use pot-hoc analysis.

Efficacy endpoints:

Time to sustained clinical improvement (as defined earlier).

Safety Endpoints

The safety endpoints of adverse events and tolerability will be assessed by review of all safety parameters, including adverse events.

	MGC Pharma Clinical Study Protocol	Protocol No.: MGC-009
		Version 02, 05 Sep 2021
		Page 63 of 76
A Phase IIb, double blind, placebo-controlled clinical study designed to evaluate the effect of CimetrA in patients diagnosed with COVID-19		CONFIDENTIAL

The incidence of adverse events will be assessed as a function of severity and association to the device. The time of resolution of the adverse events and need for treatment will also be analyzed.

Analysis Sets

The ITT analysis set will serve as the main set for safety assessments.

The primary and secondary performance efficacy assessments will also be performed on the PP and the ITT analysis sets.

Statistical Analysis

Demographic and Baseline

Demographic and baseline condition related characteristics will be tabulated and compared between the study arms by data type. Continuous variables will be summarized by a mean, standard deviation, minimum, median and maximum and categorical variables by a count and percentage.

Primary Efficacy Analysis

The primary efficacy endpoint of the study is the mean change in the WHO Ordinal Scale. It will be evaluated using a General Linear Model ANOVA test.

Subset Analyses

The primary endpoint will also be evaluated stratified by center using a General Linear Model ANOVA test.

A sensitivity analysis of the primary endpoint will be performed to assess the impact of missing data on the study outcome.

Adjustment for other covariates such as demographics or other baseline participant characteristics may be performed by adding these variables into a multivariate linear regression.

Secondary Efficacy Analysis

	MGC Pharma Clinical Study Protocol	Protocol No.: MGC-009
		Version 02, 05 Sep 2021
		Page 64 of 76
A Phase IIb, double blind, placebo-controlled clinical study designed to evaluate the effect of CimetrA in patients diagnosed with COVID-19		CONFIDENTIAL

The 3 groups will be compared with the ANOVA test or Kruskal Wallis non-parametric test, following by post-hoc analysis for pairs differences.

Additional Efficacy Parameters of Interest

A count and percentage of participants responding to each of the exploratory efficacy endpoints will be presented. The groups will be compared with a chi-squared test or a Fisher’s exact test.

Safety Analysis

The primary safety variable, the cumulative incidence (and 95% CI) of device related adverse events (AEs) throughout the study, will be presented in tabular format and will include incidence tables by severity.

Serious adverse events, device-related SAEs, adverse events (by type and overall), device-related AE, adverse device reactions and device malfunction rates will be compared between the study arms with a Fisher’s exact test.

Serious adverse events will be listed and discussed individually.

PK test

Actual times of dosing and blood collection at various time points will be recorded in source documents as well as CRF’s. Objectives of PK sampling are to measure values of CimetrA active ingredients in plasma at different time point after first administration of study medications and at different time point after multiple administrations during steady state.

PK samples will be processed and frozen on site. Labels have been prepared for the site again containing patient No., visit No., type of test (PK) and time point. Upon completion of the study, samples will be sent to selected analytical laboratory with dedicated courier service. The PK parameters will be obtained from plasma concentration data for curcumin and boswellia.

	MGC Pharma Clinical Study Protocol	Protocol No.: MGC-009
		Version 02, 05 Sep 2021
		Page 65 of 76
A Phase IIb, double blind, placebo-controlled clinical study designed to evaluate the effect of Cimetra in patients diagnosed with COVID-19		CONFIDENTIAL

Analyses of PK data will be based on the PK Set, which will include all subjects who received at least one treatment and for whom concentration data is available.

Plasma concentration data will be tabulated and plotted for each subject for whom concentrations are quantifiable and for each treatment group. Actual times of sample collection will be used. PK analysis will be performed using appropriate non-compartmental techniques to obtain estimates of the following standard PK parameters if deemed possible:

- Maximum observed serum drug concentration (C_{max})
- Time to C_{max} (t_{max})
- Lag time to start of absorption (T_{lag})
- Area under the plasma drug concentration-time curve (AUC) from time 0 to the last quantifiable concentration (AUC_{0-t})
- AUC from time 0 to infinity ($AUC_{0-\infty}$)
- Percentage of $AUC_{0-\infty}$ extrapolated (AUC_{ext})
- Apparent total volume of distribution at the terminal phase (V_z/F)
- Apparent total body clearance (CL/F)
- Terminal elimination rate constant (λ_z)
- Apparent terminal elimination half-life ($t_{1/2, z}$)
- Dose normalized C_{max} , $AUC_{0-\infty}$, AUC_{0-t}

Details of storage, handling and shipping of blood samples will be described in a Laboratory Manual.

Randomization and stratification.

	MGC Pharma Clinical Study Protocol	Protocol No.: MGC-009
		Version 02, 05 Sep 2021
		Page 66 of 76
A Phase IIb, double blind, placebo-controlled clinical study designed to evaluate the effect of Cimetra in patients diagnosed with COVID-19		CONFIDENTIAL

Subjects would be assigned in sets of four as one per each of the four study groups – this would assure that we maintain exact balance among groups in terms of n / group.

Stratification will be performed according to the medical history and risks factors, based on the data will be received in the study.

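### The hypothesis lets a significant difference demonstrate a favourable safety profile, but the test and success rule carry no safety criterion beyond WHO-scale ventilation and death, and the claimed safety precision has no calculation behind it

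*Protocol*

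**What the plan says.** All of this is in Protocol section 17 unless noted.

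- **Statistical Hypothesis.** CimetrA at both doses is expected to be more effective "while maintaining a favorable safety profile. This will be demonstrated by a significant difference between the two active and the control groups".
- **Formal test.** The null is equality of the three Deltas, and the alternative is "H1: at least one is different". The variable is defined in one line: "Where Delta is the difference between baseline and end of study in WHO Ordinal Scale for clinical trial".
- **Success rule.** "If the null hypothesis is rejected in favor of the alternative hypothesis the study will be deemed successful".
- **Safety, same subsection.** "Safety will be assessed by adverse events, blood and urine laboratory assessments and vital signs". This names data sources and gives no criterion.
- **Planned Sample Size.** The calculation is an ANOVA on the WHO scale ("We expect medium effect ($f=0.20$) for the differences in Delta between the 3 groups, and standard deviation of 1.5"), with 80 per arm and 240 in total. It closes with "For 80 participants per group we ensure the desired precision for phase 3 trial to assess safety and effectiveness".
- **Safety Endpoints and Safety Analysis.** These plan a review of all safety parameters, cumulative incidence of related adverse events (AEs) with a 95% CI, tables by severity, and individual discussion of serious AEs (SAEs). The between-arm comparison covers SAEs, AEs and related events, and its list ends "adverse device reactions and device malfunction rates will be compared between the study arms with a Fisher’s exact test". The device vocabulary does not fit a drug trial, but AEs and SAEs are clearly included.
- **Section 9.1.** Safety is listed among the primary outcomes.

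**The concern.** The hypothesis has an efficacy half and a safety half, and one sentence says how it will be demonstrated: by a significant difference between active and control. That works for efficacy. It cannot work for safety, because a significant difference in AEs would more likely signal harm, and a significant difference on the WHO scale says little about AEs, laboratory values or vital signs. The success rule then turns on the WHO scale alone.

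What is at stake is the wording of the conclusion. A report that follows the protocol literally could state that the hypothesis, safety included, was demonstrated once the F test rejects. If the report looked to the safety tests for support, a non-significant Fisher result on uncommon events would be weak evidence that safety was maintained. The sentence on precision encourages over-reading, because it says that 80 per group is enough to assess safety when only the efficacy endpoint was used to size the trial.

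**Working it through.** **1. The stated sample size.** Inputs from Planned Sample Size: three groups, f = 0.20, alpha 0.05, 80 per group. The noncentrality is f² × N = 0.04 × 240 = 9.6. The noncentral F distribution with 2 and 237 degrees of freedom gives power 79.3%, and 82 per group is the first size to reach 80%. This agrees with the stated figure of at least 80% to within a point. The calculation contains no safety quantity.

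**2. Power of the named safety test.** The protocol gives no AE or SAE rate, so control rates from 1% to 40% were assumed. The figures below are exact power of the two-sided 5% Fisher test to detect a doubling, by enumerating both binomial distributions and counting only rejections in the harmful direction. The last column pools the two active arms.

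| Control v active | 80 v 80 | 80 v 160 |
|---|---|---|
| 1% v 2% | 0.3% | 0.2% |
| 2.5% v 5% | 4% | 7% |
| 5% v 10% | 14% | 21% |
| 10% v 20% | 35% | 48% |
| 12.5% v 25% | 46% | 61% |
| 15% v 30% | 56% | 71% |
| 20% v 40% | 75% | 89% |
| 30% v 60% | 96% | 99% |

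At 80 v 80 the 50% point lies between 12.5% (45.7%) and 15% (56.3%). Linear interpolation gives 12.5 + 2.5 × (50 − 45.7)/(56.3 − 45.7) ≈ 13.5%. With pooled active arms it is just above 10%.

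The three-arm Fisher test (20,000 simulations per scenario, one or both active arms doubled) has power 19-20% at a 5% control rate, 41-44% at 10%, 64-65% at 15% and 82% at 20%. Its 50% point therefore lies between 10% and 15%.

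For scale, 80% power for a doubling needs about 435 per arm at 5% v 10%, 199 at 10% v 20% and 82 at 20% v 40% (normal approximation, no continuity correction).

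**3. Precision at 80 per arm.** The 95% half-width for a risk difference, with both arms near rate p, is 1.96 × √(2p(1 − p)/80).

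- p = 5%: 1.96 × √(0.095/80) = ±6.8 points
- p = 10%: 1.96 × √(0.18/80) = ±9.3 points
- p = 20%: 1.96 × √(0.32/80) = ±12.4 points

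With no events in one arm of 80, the exact two-sided 95% upper limit is 1 − 0.025^(1/80) = 4.5%.

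**4. What the success rule contains.** The WHO scale in section 9.1 scores mechanical ventilation at 6 and 7 and death at 8, so those outcomes enter Delta. Other AEs, laboratory tests and vital signs do not.

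**The case against.** The strongest reply is that the hypothesis sentence is only loosely drafted. Its natural subject is greater effectiveness, and the same subsection says separately that safety is assessed from AEs, laboratory tests and vital signs. That is a fair reading, and no passage says outright that a WHO-scale difference proves safety. But the sentence does place the safety clause inside what will be demonstrated, and the separate line supplies no criterion to replace it.

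Three stronger inferences are tempting, and the protocol does not support them.

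- **That a harmful dose could be declared safe.** There is no rule for calling a dose safe, and nowhere is a non-significant Fisher test treated as proof of safety. A safety judgement can also draw on the incidence CI, the severity tables and the SAE review.
- **That Fisher's test misses a doubling most of the time.** This depends on the event rate. It fails at 20% v 40%, and all-cause AEs in hospitalised COVID-19 patients may be that common. Section 13.3 reports no drug-related AEs in the 50-patient study of the old formulation. That suggests low rates for related events but does not fix them.
- **That no safety information enters the success rule.** Ventilation and death do.

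Low power for uncommon harms is ordinary in a Phase IIb trial sized on efficacy and is not an error. Per-dose intervals could also properly be left to a statistical analysis plan, so their absence alone would not be a finding. What stands is what the protocol does state: the demonstration sentence, a success rule without a safety criterion, and an assurance of precision. A later plan should not have to contradict these.

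**Conclusion.** The point holds in limited form. The hypothesis includes safety in what a significant difference will demonstrate, while the formal test and success rule contain no safety criterion beyond the ventilation and death categories of the WHO scale. The assurance about safety precision rests on no safety calculation and states no target, so it is unsupported rather than shown to be false. It also refers to a phase 3 trial, although this one is Phase IIb.

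The size of the problem depends on assumed event rates. Below a control rate of about 13-14% (80 v 80), a doubling would be missed more often than found, so for uncommon events, such as drug-related AEs may prove to be, non-significance would not support maintained safety. Above that rate the test does better than even. The correction should be made because it governs what a positive result may be said to prove; it does not affect the validity of the efficacy test.

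**What to change.** - **Statistical Hypothesis.** Limit the demonstration by a significant difference, and the success rule, to efficacy. State the safety aim separately.
- **Safety Analysis.** For each active dose against placebo, add the risk difference with a 95% CI for participants with at least one study-drug-related AE, any AE and any SAE. State that the safety conclusion rests on these estimates together with the review already planned, and not on non-significant p-values.
- **Planned Sample Size.** Replace the precision sentence with what 80 per group delivers: about ±7, ±9 and ±12 points for a difference at event rates of 5%, 10% and 20%, and an upper limit of 4.5% when an arm of 80 has no events.

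The cost is protocol wording and a few intervals from data already collected, with no added patients or procedures. The price is a more modest safety claim.

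### Success is declared when a direction-free three-arm F test rejects, so neither CimetrA dose has to beat placebo and harm can count as success

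*Protocol*

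**What the plan says.** Under the Statistical Hypothesis heading of Protocol section 17 the aim is directional: "treating with CimetrA and CimetrA2 will be more effective, while maintaining a favorable safety profile". It continues: "This will be demonstrated by a significant difference between the two active and the control groups".

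The formal hypotheses follow. The null is equality of the three Deltas. Delta is defined thus: "Where Delta is the difference between baseline and end of study in WHO Ordinal Scale for clinical trial". The alternative is "H1: at least one is different". The decision rule is "If the null hypothesis is rejected in favor of the alternative hypothesis the study will be deemed successful".

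The sample size is built on the same omnibus test, a one-way fixed-effects ANOVA with three levels, and adds "The analysis of variance is two-tailed Main effects". The Primary Efficacy Analysis is a general linear model ANOVA of the mean WHO change.

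Comparisons between pairs of arms appear in two places. Under Significance Levels and Handling of Type I Error, the remedy for multiple comparisons is "therefore we will use pot-hoc analysis". Under Secondary Efficacy Analysis, post-hoc tests of pairs follow the three-group test. Neither place makes a dose-versus-placebo result a condition of success.

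**The concern.** The aim and the rule, a few lines apart, are different statements. The aim is that CimetrA is better than control. The rule asks only whether the three means are unequal. Three kinds of result meet the rule without supporting the aim:

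- one or both doses are worse than placebo;
- the two doses differ from each other but neither is distinguishable from placebo;
- the F test rejects but no single contrast can be named as the reason.

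At stake is the trial's main conclusion. Under this text the sponsor could report a successful study with no evidence of benefit, or because of harm. Section 12.1 says the additional dose arm was included for dose finding, and a rejected omnibus null does not identify a dose. The hypothesis also refers to a favourable safety profile, and no safety condition enters the rule.

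**Working it through.** **Inputs (Protocol section 17, Planned Sample Size).** Three arms, 80 per arm, N = 240, f = 0.20, SD 1.5. The significance criterion "has been set at 0.05 with Power of at least 80" percent. A lower WHO score is better, so a negative change is an improvement.

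**1. The plan's own figure.** Noncentrality is N × f² = 240 × 0.04 = 9.6, with 2 and 237 degrees of freedom and a critical F of 3.034. Power is 79.3%. It first exceeds 80% at 82 per arm (80.4%). The sample size therefore reproduces to within rounding, and the problem is not in that arithmetic.

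**2. Why direction drops out.** The noncentrality is n × Σ(arm mean − overall mean)² / SD². Squaring removes the sign, and the sum does not depend on which arm is placebo. Every pattern of means with f = 0.20 has the same 79.3% chance of success.

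**3. Patterns that give f = 0.20.** The SD of the arm means is 0.20 × 1.5 = 0.30 points.
- One arm differs from the other two by d: 0.30 = d√2/3, so d = 0.64.
- Equally spaced arms with range r: 0.30 = r/√6, so r = 0.73 and half of it is 0.37.

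The Protocol gives f but no arm means, so these patterns are assumptions.

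**4. Two worked results** (F = n × variance of the arm means / SD²; placebo last).
- Mean changes −0.4, −1.0, −1.0: variance 0.12, F = 80 × 0.12 / 2.25 = 4.27, p = 0.015. This is a success in which one dose is worse than placebo and the other equals it.
- Mean changes −1.3, −0.7, −1.0: variance 0.09, F = 80 × 0.09 / 2.25 = 3.20, p = 0.043. This is a success, yet each dose differs from placebo by 0.3 / (1.5 × √(2/80)) = 0.3 / 0.237 = 1.26 standard errors, p = 0.21.

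**5. Simulation.** Normal data with no dropout, and a two-sided Dunnett critical value of 2.225 (two comparisons, 237 df). All entries are percentages of all trials.

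| True effect against placebo | Success by F | F success, no dose better (Dunnett) | Same, unadjusted t | At least one dose better (Dunnett) | Both doses better (Dunnett) |
|---|---|---|---|---|---|
| Both better by 0.64 | 79 | 0.3 | <0.1 | 82 | 53 |
| Linear: 0.73 and 0.37 better | 79 | 1.1 | 0.4 | 82 | 24 |
| One better by 0.64, other equal | 79 | 13 | 8 | 68 | 1 |
| One better, one worse, by 0.37 | 79 | 54 | 46 | 25 | 0 |
| One worse by 0.64, other equal | 79 | 78 | 77 | 1 | 0 |
| Both worse by 0.64 | 79 | 79 | 79 | 0 | 0 |

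In the fourth row, 31% of trials are successes in which neither dose differs from placebo in either direction by Dunnett (19% by unadjusted t tests).

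**The case against.** The best defence is that section 17, read whole, shows what was meant. The aim names both the direction and the comparator, the hypotheses look like a standard ANOVA template, and pairwise tests are planned. Nobody would present harm as success. The patterns with harm are chosen by the reviewer, and when both doses help, or the response is linear, the F test almost never succeeds without a dose being better (0.3% and 1.1%). Naming a post-hoc procedure can be left to an SAP.

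Part of this stands. The intention is clear, and an unnamed procedure alone would not be a finding. Dunnett is also not the only remedy. With exactly three groups, a significant F followed by unadjusted pairwise tests controls the familywise error. With direction required, that route shows at least one dose better in 71% of trials when only one dose works (Dunnett 68%), and in 79% when both work or the response is linear (Dunnett 82%).

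It does not rescue the rule. The success sentence refers to the formal alternative and not to the prose, and even the prose asks only for a significant difference. The pairwise tests are planned but have no role in success. The Protocol did not defer this point. It stated a rule, and an SAP with another rule would contradict it. The result most likely to cause trouble is not gross harm but a significant F with both placebo contrasts inconclusive, which this text calls success.

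**Conclusion.** The concern holds and should be corrected before unblinding. The stated success rule does not test the stated hypothesis. This follows from the wording alone and needs no simulation.

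The size depends on the true pattern. At the planned f = 0.20 the rule declares success in 79.3% of trials whatever the direction. Success comes with no dose shown better than placebo in 78% of trials if one dose is worse by 0.64 points, in 54% if the doses lie 0.37 points either side of placebo, and in 13% if only one dose works. It is about 1% or less if both doses help or the response is linear. These figures assume normal changes with SD 1.5, all 240 patients analysed, and arm means chosen to match the plan's f. Worse here means a worse change on the WHO scale.

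**What to change.** In section 17, replace the success sentence. The study succeeds if at least one CimetrA dose shows a significantly greater improvement than placebo in the WHO change, tested by two Dunnett-adjusted dose-versus-placebo comparisons at two-sided 5%, with the direction required. Report the F test as supportive, and put this procedure in place of the post-hoc sentence under Significance Levels and Handling of Type I Error. If the sponsor prefers to keep the F test first, success could instead require a significant F and at least one dose significantly better than placebo.

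State the power of the comparisons that decide success: about 82% for at least one dose when both doses share the 0.64-point effect or the response is linear, and 68% for each single dose at 0.64 points. Say explicitly that the claim is at least one dose. The prose can be read as requiring both, and that claim would have only 53% power when both share the effect and 24% under a linear response.

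The cost is wording, with the same 240 patients. The real loss is in the case where only one dose works: 68% against 79% for the F test, which is below the plan's 80%. Of those 79 points, however, 13 are rejections in which no dose is shown better than placebo. When both doses are worse by 0.64 points, the chance of declaring success falls from 79% to about 0%.

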11.3. Removal of subjects from therapy or assessment

- a. If any of the inclusion criteria fails to be met, or any of the exclusion criteria is met during the period in which the interim history, physical examination and laboratory tests are performed, the subject will be ineligible to continue in the study. These subjects will be classified as screened but not enrolled.
- b. If the subject begins a regimen of medication at any time during the study that includes any of the medications listed in the exclusion criteria or begins an increase in dose of an existing regimen of medication at any time during the study, the subject will be terminated from the study. These subjects will not be used in the primary analyses.
- c. If continuing in the study does not appear to be in the best medical interest of the subject, his/her participation may be terminated by either the Principal

	MGC Pharma Clinical Study Protocol	Protocol No.: MGC-009
		Version 02, 05 Sep 2021
		Page 48 of 76
A Phase IIb, double blind, placebo-controlled clinical study designed to evaluate the effect of CimetrA in patients diagnosed with COVID-19		CONFIDENTIAL

Investigator or the study director. Removal of an individual by the Principal Investigator will be reported to the Institutional Helsinki Committee and the appropriate regulatory agencies according to the guidelines of these groups. These subjects will not be used in the primary analyses unless the reason for removal was due to reasons of safety in which case data would be used in the primary analyses.

d. In addition to a participant being able to voluntarily withdraw from the study at any time, the Investigator may withdraw participants from the study under the conditions noted below, and such subjects will not used in the primary analyses.

e. Participants will be withdrawn from the treatment protocol if participants are unwilling or unable to comply with the schedule of treatment, follow-up or safety monitoring, and will not be used in the primary analyses.

f. Subjects considered treatment failures will be removed from the study and will be offered alternative standard therapy by their treating physician and will not be used in the primary analyses.

11.4. **Screening and Enrollment logs**

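### 240 patients give about 79% power only if every randomised patient is analysed; no loss is allowed for, and section 11.3 excludes patients from the primary analyses

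*Protocol*

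**What the plan says.** **Sample size.** Protocol section 17 (Planned Sample Size), repeated in the synopsis, fixes every input. On the effect: "We expect medium effect ($f=0.20$) for the differences in Delta between the 3 groups", with a "standard deviation of 1.5, based on the ordinal scale (0-8"). On the test: "This power analysis is for a one-way fixed effects analysis of variance with 3 levels". On the number: "The study will include 80 patients per group for a total of 240 patients". Alpha is 0.05, "with Power of at least 80" per cent. No expected loss or exclusion rate is given, and the 240 is not inflated for one.

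**Exclusions.** Section 11.3 says who leaves the primary analyses after enrolment. Item (b) covers patients who start certain medications or increase the dose of an existing one, and says: "These subjects will not be used in the primary analyses". Items (c) to (f) apply the same consequence to patients removed in their medical interest (unless for safety, in which case they are kept), patients withdrawn by the investigator, non-compliant patients and treatment failures. Item (a) concerns screening failures, who are not enrolled.

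**Analysis sets and missing data.** Section 17 (Missing Data) says missing values are handled under ITT. It names multiple imputation for binary data as the main method for the primary efficacy endpoint. It uses last observation carried forward for patients with no post-baseline measurement or withdrawn for an adverse event or intolerability. Section 17 (Analysis Sets) makes ITT the main set for safety, and runs efficacy on both PP and ITT without saying which is primary.

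**The concern.** The trial is declared successful if the three-group null hypothesis is rejected, so the power of that one test determines how a negative result is read. A power floor of 80% can be relied on only if the number analysed is the number in the calculation. Here 80 per group is roughly the break-even number with nobody lost, yet the protocol has rules that remove enrolled patients from the primary analyses.

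The patients are hospitalised with moderate, possibly worsening COVID-19 and are followed to day 28, with standard care adjusted by clinical judgment. Dose changes, non-compliance and treatment failure are foreseeable in such a population. If the exclusions apply as written, the risk of missing the planned effect is higher than the protocol tells its readers.

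**Working it through.** **Inputs** (section 17, Planned Sample Size): k = 3 groups, n = 80 per group, N = 240, f = 0.20, alpha = 0.05. The SD of 1.5 is already contained in f and does not enter separately (it implies an SD of the group means of 0.20 × 1.5 = 0.30). The protocol also says "The analysis of variance is two-tailed Main effects"; the omnibus F test uses the upper tail of F at 0.05, so this label does not change the power.

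**Formula.** Power = P(F′ > Fcrit), where F′ is noncentral F with k − 1 and N − k degrees of freedom and noncentrality λ = N × f², and Fcrit is the 95th percentile of the central F with the same degrees of freedom.

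**The protocol's own figure.** λ = 240 × 0.04 = 9.6; df = 2 and 237; Fcrit = 3.034. Power = 79.3%. The large-sample chi-square approximation gives 79.8%.

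**How close this is to 80%.**
- 81 per group: 79.8%. 82 per group: 80.4%.
- At 80 per group, f = 0.2016 gives 80%. Values of f that round to 0.20 (0.195 to 0.205) give 77.1% to 81.4%.

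The stated sample size therefore reproduces to within rounding, with nothing to spare.

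**Effect of exclusions.** The loss rates are assumptions, since the protocol gives none. Analysed n per group = 80 × (1 − d), and λ = 3n × 0.04.

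| Not analysed (assumed) | n per group | λ | Power at f = 0.20 | f detectable at 80% power |
|---|---|---|---|---|
| 0% | 80 | 9.60 | 79.3% | 0.202 |
| 5% | 76 | 9.12 | 77.1% | 0.207 |
| 10% | 72 | 8.64 | 74.6% | 0.213 |
| 15% | 68 | 8.16 | 72.0% | 0.219 |

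At 10-15% not analysed, the chance of missing the planned effect is 25.4% to 28.0% (100 − 74.6 and 100 − 72.0), against at most 20% as stated.

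**Does the imputation text restore the count?** Setting section 11.3 beside section 17 (Missing Data):
- Last observation carried forward reaches only withdrawals for adverse events or intolerability and patients with no post-baseline value. It does not, as such, cover dose increases (b), non-compliance (e) or treatment failure (f).
- Multiple imputation is specified for binary data, whereas the primary endpoint in section 17 (Primary Efficacy Analysis) is a mean change on the WHO scale.
- Only section 11.3 says who is in or out of the primary analyses, and it takes patients out.

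The ITT wording and the section 11.3 wording cannot both define the primary efficacy analysis.

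**The case against.** The strongest case on the other side has three parts.

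1. **The sample size is not wrong.** This stands. A reader might infer from 79.3% that the calculation contains an arithmetic error. The document does not support that: f is given to two decimals, a value of 0.202 gives 80.2%, and the exact requirement is 82 rather than 80 per group. Uncertainty about f and the SD is far larger than 0.7 points.

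2. **Nobody need be lost.** Section 17 refers to ITT, to imputation and to efficacy on the ITT set, so all randomised patients could stay in the count. Treatment is four doses over two days in inpatients, follow-up after discharge is largely by phone, and the WHO scale scores death, so data loss may be small. This stands in part: it rules out saying that the analysed number is certain to fall below 80 per group. It does not settle the matter, because section 11.3 says the opposite about the primary analyses, ITT is named as the main set only for safety, and the imputation rules do not reach most of the section 11.3 categories.

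3. **Section 11.3 is narrower than it looks.** Item (a) is not post-enrolment loss. Item (b) partly refers to medications in the exclusion criteria, and section 11.2 lists none, so only its dose-increase part operates. Safety removals under (c) are kept, (d) is permissive, and section 11.3 does not define treatment failure for (f). All of this is fair and makes the size of the loss unknowable from the protocol. It does not make it zero.

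**Conclusion.** The point holds in a limited form. With every randomised patient analysed, power is about 79%, which is the stated 80% to within rounding. There is no margin and no stated allowance for loss, and the protocol contradicts itself on who is analysed. Under section 11.3 as written, any exclusion takes power further below the stated floor: 77.1%, 74.6% or 72.0% at assumed rates of 5%, 10% or 15%. Under a full ITT analysis with a usable value for each of the 240, it stays at about 79%.

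The figures rest on the protocol's f = 0.20 and alpha 0.05, and on exclusions spread equally over the three arms without changing f. The loss rates are illustrative only. The document supports neither a claim that the calculation is in error nor a claim that a shortfall of a particular size will occur.

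**What to change.** Keep N = 240 and make two changes.

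1. **Reconcile section 11.3 with section 17 (Missing Data, Analysis Sets).** State that the primary efficacy analysis is ITT and includes all randomised patients, and that the exclusions in section 11.3 (b) to (f) apply to the PP set only.

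2. **Restate the power in section 17 and the synopsis.** For example: with f = 0.20 and alpha 0.05, power is about 79% if all 240 patients are analysed, and about 72-75% if 10-15% are not (assumed rates). Alternatively, give the f detectable with 80% power: about 0.202 with no loss, 0.213 at 10% and 0.219 at 15%.

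The cost is a few sentences in sections 11.3 and 17 and the synopsis, and a slightly less favourable power statement. No patients are added and the design does not change.
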